### 6.6. Safety Summaries and Analyses

Safety data will be summarized according to current Pfizer data standards including incidence of anti-drug antibodies and neutralizing antibodies by week 97. At the screening visit, the “Children’s Baseline/Screening” assessment from the Columbia Suicide Severity Rating Scale will be performed. At all other visits the “Children’s Since Last Visit” assessment will be performed. If there is endorsement of ideation or suicidal behavior a Risk Assessment will also be reported. *In subjects randomized to Sequence 1, long term safety will be evaluated within subjects as compared to baseline for all safety endpoints previously described through Week 97.*

Subject evaluation groups will show end of study subject disposition and will show which subjects were analyzed for efficacy (FAS or PPAS), pharmacokinetics (PK), and safety (adverse events and laboratory data). Frequency counts will be supplied for subject discontinuation(s) by treatment. Data will be reported in accordance with the sponsor reporting standards.

A breakdown of demographic data will be provided for age, race, weight, body mass index, and height. Each will be summarized by treatment sequence in accordance with the sponsor reporting standards.

The following data will also be summarized by treatment and in accordance with the current sponsor reporting standards:

Discontinuations, adverse events, laboratory data, vital signs, ECG and concomitant medication data will be summarized by treatment and in accordance with current Pfizer data standards.

Safety analyses will be based on the safety analysis set.

### **6.6.1. Adverse Events**

All adverse event summaries will be presented for the complete study (period 1 and period 2). Additionally, summary tables of the most frequent adverse events will be presented by period and/or by 4-month dosing intervals. Based on the review of the frequency and timing of adverse events, additional summaries may be requested.

Using the 3-tier approach, summaries will be created using the risk difference. No adjustment for multiplicity will be made. Tables and graphs will be produced for tier-1 and tier-2 events. For tier-1 events, point estimates, confidence intervals for the risk difference and p-values will be shown. For tier-2 events, point estimates and confidence intervals will be produced. AEs will be sorted in descending order of the risk difference. Comparisons of the active treatment overall and the individual dose levels to the placebo group will be made. Default footnotes should be included to describe the proper interpretation of p-values and confidence intervals for the risk difference.

It should be recognized that most studies are not designed to reliably demonstrate a causal relationship between the use of a pharmaceutical product and an adverse event or a group of adverse events. Except for select events in unique situations, studies do not employ formal adjudication procedures for the purpose of event classification. As such, safety analysis is generally considered as an exploratory analysis and its purpose is to generate hypotheses for further investigation. The 3-tier approach facilitates this exploratory analysis.

An exposure adjusted analysis may be performed, particularly if there are suggestions of differences between event rates for subjects with long term PF-06252616 exposure (Sequence 1) and those with placebo and active treatments (Sequences 2 and 3).

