Exposure from the first 12 subjects will be reviewed to confirm that the exposure in the pediatric population is consistent with model predictions from the healthy adult volunteer study. This will occur following at least one dose at the 5 mg/kg dose level and will occur again following at least one dose at 20 mg/kg dose level. Should there be any clinically relevant differences in exposure versus those predicted; a dose adjustment may be made as agreed with the E-DMC. This analysis will be performed by a group of unblinded Clinical Pharmacology scientists not directly involved in the day to day conduct of the study. It is planned that recruitment would continue during this evaluation period.

The study will remain double-blinded until the time of the primary analysis for safety and efficacy (after the last enrolled subject completes 49 weeks). At that time, a limited number of study team members will be unblinded to the treatment assignments. The sites (with the exception of unblinded site personnel eg, the pharmacist) and the subjects will remain blinded to their study treatment through the conclusion of the study.

The following is a schematic of the study design.

Note: Sequence 1, Period 2 demonstrates subjects continuing on the maximum tolerated dose from Period 1 for each individual subject, as per the dose adjustment criteria (Table 2). SCRN=Screening, PBO=Placebo, W=Weeks

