### 3.5. Safety Endpoints

#### 3.5.1. Adverse Events

All adverse events will be reported under the treatment last received prior to the onset of the adverse event.

A 3-tier approach will be used to summarize AEs. Under this approach, AEs are classified into 1 of 3 tiers. Different analyses will be performed for different tiers (See 8.2.3).

Tier-1 events: These are pre-specified events of clinical importance and are maintained in a list in the product's Safety Review Plan (GDMS Location: /Compounds/PF-06/PF-06252616/Product Strategy and Administration/Product Strategy/Safety Review Plan or see link for current version: <http://gdms.pfizer.com/gdms/drl/objectId/090177e18692171a>)

Tier-2 events: These are events that are not tier-1 but are "common". A MedDRA PT is defined as a tier-2 event if there are 4 or more subjects with the same PT in any one treatment group, given the trial will have less than 400 or fewer subjects per treatment group ("Rule of 4").

Tier-3 events: These are events that are neither tier-1 nor tier-2 events. Pfizer standard safety output where all AEs will be included (ie, no new outputs).

Severity is the key baseline information for adverse events. To judge an increase in adverse event severity after dosing, the post-dosing adverse event severity will be compared to the adverse event severity reported prior to the first day of study drug administration.

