### 5.2. General Methods

*Continuous variables will be summarized by the N, mean, median, standard deviation, minimum and maximum. Categorical variables will be summarized by percent and counts. All summaries will be displayed by treatment group, and/or sequence, and/or period depending on the endpoint. Efficacy data will be listed, tabulated and graphically represented, as appropriate. Model assumptions will be tested using appropriate statistical or graphical techniques.*

All plots produced may be used as in-text plots in the CSR and therefore need to be optimized for inclusion, ie, legends, axis labels and titles should be clearly legible when inserted into one half of a page within the CSR.

To explore the data further and to assess the goodness-of-fit of all statistical models, separate SAS datasets will be provided by the clinical programmer to the statistician. Covariates for data exploration may include baseline and/or demographic covariates such as gender, age, weight (continuous and/or Pfizer standard categorical cut-offs), site, country, steroid usage, 4SC at baseline, etc.

*Change from baseline in functional assessments will be analyzed using a longitudinal mixed effects model, or mixed-effect model for repeated measures(MMRM). The baseline result, treatment, time and treatment by time interaction will be included as fixed effects in the model. The stratification factor of time to complete the 4 stair climb at baseline will be included in the model, see [Section 6.1.1](#), unless the baseline time to climb 4 stairs is included in the model. Subject will be included as a random effect and the model will be fit with an unstructured covariance for the repeated measures. If there are model convergence issues when using an unstructured covariance, then compound symmetry and autoregressive covariance structures will be explored to potentially address convergence issues and model fit. The distribution of the time to complete the functional assessment is assumed to be right skewed.*

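### SAP 6.6.1 puts the adverse-event risk differences against placebo on the complete study, where exposure is unequal, and does not commit to a Period 1 version

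*SAP*

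**What the plan says.** **Protocol.** Section 2.2.1 bases primary safety on Period 1 and asks for TEAE incidence by Week 49. It names no comparator for AEs. Section 3.1 schedules a "primary analysis for safety and efficacy (after the last enrolled subject completes 49 weeks"). Section 9.3.5 plans tables and listings of AE data without formal statistical analysis.

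**SAP 3.5.1.** "All adverse events will be reported under the treatment last received prior to the onset of the adverse event". AEs fall into three tiers: tier 1 is a list of clinically important events kept in a Safety Review Plan, and tier 2 is any other preferred term reported by at least 4 subjects in one treatment group.

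**SAP 6.6.1.** The window is set first: "All adverse event summaries will be presented for the complete study (period 1 and period 2"). In addition, "summary tables of the most frequent adverse events will be presented by period and/or by 4-month dosing intervals". The section then specifies risk differences with confidence intervals for tiers 1 and 2, p-values for tier 1, and no multiplicity adjustment. The contrasts are given as "Comparisons of the active treatment overall and the individual dose levels to the placebo group will be made". Allowance for exposure is optional: "An exposure adjusted analysis may be performed, particularly if there are suggestions of differences between event rates".

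**General rules.** SAP 5.2 says "All summaries will be displayed by treatment group, and/or sequence, and/or period depending on the endpoint". SAP 6.6 says AE data "will be summarized by treatment and in accordance with current Pfizer data standards".

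**The concern.** The paragraph of SAP 6.6.1 that defines the risk differences names no window of its own, so the complete-study window set at the start of the section applies. Over the complete study the groups are not observed for equal time. Sequence 1 is on active for both periods, Sequences 2 and 3 spend one period on each treatment, and each dose level below the top is planned for only 16 weeks. A crude proportion rises with time at risk, so differences appear with no drug effect, and they run in opposite directions for active overall and for the dose levels.

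AEs are to be sorted by these differences, and tier-1 events carry p-values. At stake are a biased overall difference and a misleading dose pattern in the tables from which readers will judge safety. The randomised comparison with equal planned exposure exists in Period 1, but no sentence commits to tier-1 or tier-2 risk differences there.

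**Working it through.** **Inputs.** Three sequences of 35 boys, two periods of about 48 weeks, and four doses over 16 weeks per level (protocol 3.1, Tables 3 and 4); attribution to the last treatment received (SAP 3.5.1). SAP 6.6.1 gives no figure of its own. The planned duration reproduces: 12 doses x 4 weeks = 48 per period, and 24 x 4 = 96 in total.

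**Weeks at risk, full completion and full escalation**

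| Group | Seq 1 | Seq 2 | Seq 3 | Boys | Mean weeks |
|---|---|---|---|---|---|
| Active overall | 96 | 48 | 48 | 105 | 64 |
| Placebo | none | 48 | 48 | 70 | 48 |
| 5 mg/kg | 16 | 16 | 16 | 105 | 16 |
| 20 mg/kg | 16 | 16 | 16 | 105 | 16 |
| 40 mg/kg | 16 + 48 = 64 | 16 | 16 | 105 | 32 |

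In person-weeks, active has 35 x 192 = 6,720 and placebo 35 x 96 = 3,360. The ratio of mean exposure is 64/48 = 1.33. Counting follow-up to Week 105 under the last treatment gives 69.3 against 52.0 weeks, again 1.33. The 70 boys of Sequences 2 and 3 count in both groups, and no method for that dependence is stated.

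**Risk for an inert drug.** Assume a constant hazard and a 48-week risk p, so that r(w) = 1 - (1 - p)^(w/48). Then:

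- placebo = r(48) = p
- active overall = [r(96) + 2 r(48)]/3
- 5 and 20 mg/kg = r(16)
- 40 mg/kg = [r(64) + 2 r(16)]/3

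At p = 0.20: r(96) = 0.360, r(64) = 0.2574 and r(16) = 0.0717. Active overall is (0.360 + 0.400)/3 = 0.253, and 40 mg/kg is (0.2574 + 0.1434)/3 = 0.1336.

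| Assumed 48-week risk | Active overall | 5 and 20 mg/kg | 40 mg/kg |
|---|---|---|---|
| 2% | +0.65 | -1.33 | -0.67 |
| 5% | +1.58 | -3.30 | -1.67 |
| 20% | +5.33 | -12.83 | -6.64 |

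Entries are percentage points against placebo; the correct value is 0 throughout.

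**Period 1 only.** Both arms have 48 weeks, so the overall difference is r(48) - r(48) = 0 for any p. A dose level would still set 16 weeks against 48, so Period 1 alone does not repair the dose-level rows. They need placebo from the same 16-week block.

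**Escalation pattern.** If 40 mg/kg were closed throughout, 20 mg/kg would be [r(80) + 2 r(32)]/3, and its shift at p = 0.20 falls to -0.4 points.

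**A true excess.** Suppose the hazard is tripled at 5 mg/kg only. That row becomes r(3 x 16) - r(48) = 0. Active overall at p = 0.20 becomes [r(128) + 2 r(80)]/3 - r(48) = +15.7 points, and a Period 1 comparison gives r(80) - r(48) = +11.1.

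**The case against.** **A Period 1 table may well appear.** Protocol 2.2.1 stays in force, protocol 3.1 schedules a primary safety analysis, SAP 5.2 allows display by period, and SAP 6.6.1 promises split tables for the commonest events. All true. But protocol 3.1 fixes timing and not a table, SAP 5.2 is permissive, and the split tables may be by 4-month interval only. Tier-1 events are chosen for importance and not frequency, so they need not be in those tables.

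**Unseen sources.** Sponsor data standards and the Safety Review Plan might supply the table. SAP 3.5.1 also points to a Section 8.2.3 for the tier analyses, which this SAP does not contain. This limits confidence; it does not supply a commitment.

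**Safety analysis is exploratory.** SAP 6.6.1 says so and requires interpretive footnotes. That lowers the stakes, but it does not remove a shift in a known direction.

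**Denominators are not defined.** SAP 5.1, written for efficacy, takes placebo as Sequence 3 in Period 1. Restricting placebo alone in that way leaves the figures unchanged, because its risk is still r(48). Restricting active to Period 1 as well would bring the overall shift to 0. The overall figures therefore rest on active including Period 2, as the plain reading has it.

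**Noise.** At 5% risk the overall shift of +1.6 compares with a standard error of about 3.6 points, treating the groups as independent. This stands for rarer events. The dose-level shift of -3.3 against about 2.9 is not negligible. The largest shifts concern common events, which are the likeliest to get split tables.

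**Stronger readings.** A reader might infer that the primary safety endpoint itself requires a comparison with placebo. It does not: protocol 2.2.2 names placebo for the stair climb, while 2.2.1 names no comparator for AEs. The contrast comes from SAP 6.6.1. A reader might also infer that a safety signal would vanish. The tripled-hazard case shows that an excess lost in its own row can still appear in active overall, and the E-DMC reviews unblinded safety data throughout.

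**Conclusion.** The point holds as a matter of analysis choice. Read plainly, SAP 6.6.1 compares groups with mean exposure of 64 and 48 weeks overall. Under full escalation it also sets 16 or 32 weeks at a dose level against 48 on placebo. For an inert drug this gives about +1.6, -3.3 and -1.7 points (active overall, 5 and 20 mg/kg, 40 mg/kg) at an assumed 48-week risk of 5%, and +5.3, -12.8 and -6.6 at 20%.

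The sizes are illustrative. They assume a constant hazard, full completion and full escalation, active and placebo pooled over both periods, and AE rates that the documents do not give. The upward shift overall follows from the sequences. The dose-level shifts depend on how many boys escalate.

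A Period 1 tier-1 or tier-2 risk difference is possible but not committed to. The documents do not support saying that it will be absent. Separately, the tier-1 p-values sit awkwardly with protocol 9.3.5 and the two need reconciling.

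**What to change.** 1. Run the tier-1 and tier-2 risk differences on Period 1 (first dose to Week 49 pre-dose), Sequences 1 and 2 together against Sequence 3 as randomised, and label them exploratory.
2. Present whole-study and Period 2 AEs descriptively by sequence, with exposure-adjusted rates as a definite analysis. Show Sequence 2 Period 2 separately from Period 1 placebo: SAP 6.3.1.3.1 uses samples from that time to estimate the half-life of the drug, so measurable drug is expected. No effect on AE rates is claimed.
3. Compare each dose level with placebo in the same 16-week block of Period 1, with exposure-adjusted rates by dose actually received alongside.
4. Reconcile the tier-1 p-values with protocol 9.3.5.

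**Cost.** SAP wording and table shells only; no new data. Period 2 events leave the risk-difference tables. Blocks by planned dose dilute a true dose effect when boys are not escalated: with 20% not at 40 mg/kg in that block, a tripled hazard at 20% 48-week risk would show 0.8 x 12.8 = 10.3 points instead of 12.8. That is why rates by dose received belong beside them.

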### Sequence 1 (n=35):

Period 1: Active treatment (PF-06252616) within subject dose escalation (5, 20 and 40 mg/kg)

Period 2: Active treatment (PF-06252616) at the maximum tolerated dose in Period 1

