**Sequence 2 (n=35):**

Period 1: Active treatment (PF-06252616) within subject dose escalation (5, 20 and 40 mg/kg)

Period 2: Placebo

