**Sequence 3 (n=35):**

Period 1: Placebo

Period 2: Active treatment (PF-06252616) within subject dose escalation (5, 20 and 40 mg/kg)

Each dose level will be explored in a dose escalating fashion within subjects, starting with the lowest dose. At each dose level, dosing will be administered over a 2-hour IV infusion every 4 weeks for a total of 16 weeks (4 doses). Dose escalation within a subject will occur following review of all available safety data through the planned fourth dose within each dose level. For example, in Period 1, there are three times when individual safety data will be reviewed for a determination of dose adjustment, at Week 13, Week 29 and Week 45 (every 4 months). In Period 2, there are two times when individual safety data are reviewed for a determination of dose adjustment, at Weeks 61 and 77 (every 4 months). Subjects will move from Period 1 to Period 2 without a pause between periods.

[figure not shown]
Subjects who complete this study through Week 97 may be invited to participate in an open-label-extension (OLE) study. Subjects, who have had a positive test result for ADA at any point during the study, *may* be asked to complete additional immunogenicity testing if warranted by other clinical safety findings prior to joining an extension study.

During the study, additional visits will be required to fully characterize PK and safety when subjects would not otherwise be returning for study drug administration. In order to limit the burden of the additional PK/safety assessments, only the first 12 subjects enrolled in the study will be asked to complete these additional PK visits. At each dose level, the first 12 subjects will be asked to return for testing 1 week after the first dose within each level and once again at 1 week after the last dose at each dose level. The additional PK/safety assessments will occur 6 times in Period 1. No additional visits would be required for these subjects in Period 2.

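### Complete-study adverse event comparisons put the same boys in both the active and placebo columns, and the SAP names no variance method or required exposure handling that fits

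*SAP*

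**What the plan says.** SAP 6.6.1 sets the scope: "All adverse event summaries will be presented for the complete study (period 1 and period 2"). Within that scope, "Comparisons of the active treatment overall and the individual dose levels to the placebo group will be made". On inference it says "For tier-1 events, point estimates, confidence intervals for the risk difference and p-values will be shown", and "For tier-2 events, point estimates and confidence intervals will be produced". There is no multiplicity adjustment. SAP 3.5.1 fixes the attribution: "All adverse events will be reported under the treatment last received prior to the onset of the adverse event".

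The design (Protocol 3.1; SAP 2.2) has three sequences of 35 boys. Sequence 1 is on active in both periods. Sequence 2 is on active first, then "Period 2: Placebo". Sequence 3 starts with "Period 1: Placebo", then goes to active. Each period lasts about 48 weeks.

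Three further statements in SAP 6.6.1 matter. By-period tables are promised only for the most frequent events, and may instead be split by 4-month dosing interval. An exposure-adjusted analysis is optional. Safety analysis is described as generally exploratory.

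No test, interval method or variance estimator is named for the risk difference. SAP 3.5.1 points to a section 8.2.3 for the tier analyses, but section 8 of this SAP is the reference list. SAP 6.6 defers to the sponsor's data standards.

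**The concern.** A risk difference between an active and a placebo group is normally computed as if the groups were different people. Here a boy in Sequence 2 or 3 is counted once in each column. If boys prone to an event (a fall or an infection, say) tend to have it in both periods, the two column proportions are positively correlated. A two-group formula then uses the wrong standard error, so the intervals for tiers 1 and 2 and the p-values for tier 1 do not have their stated properties.

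The same overlap arises for each dose level, because as planned the boys of Sequences 2 and 3 pass through every dose level as well as placebo. The efficacy model in SAP 5.2 handles repeated measures explicitly; the adverse event section has no counterpart. Safety is a primary objective of this first-in-patient study, and these are the only inferential adverse event displays that the SAP guarantees.

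**Working it through.** **Inputs.** Sequence sizes 35, 35 and 35 and periods of about 48 weeks (Protocol 3.1). Pooling of periods (SAP 6.6.1) and attribution by treatment last received (SAP 3.5.1). The documents give no adverse event rate, no within-boy correlation and no power or precision for this comparison, so there is no planned figure to reproduce. Event rates and rho below are assumptions.

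**Step 1: the columns.** Active = 35 + 35 + 35 = 105 (Sequence 1 in both periods, Sequence 2 in Period 1, Sequence 3 in Period 2). Placebo = 35 + 35 = 70 (Sequence 2 in Period 2, Sequence 3 in Period 1). Shared = 70. These are planned maxima.

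**Step 2: variance at equal risk p and equal exposure.**
- Two-group variance: p(1-p)[1/105 + 1/70] = p(1-p) * 0.02381.
- The overlap subtracts 2 * 70 * rho * p(1-p)/(105*70) = p(1-p) * 0.01905 * rho.
- Ratio of true to two-group variance: 1 - (0.01905/0.02381)*rho = 1 - 0.8*rho.

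| Assumed rho | True SE / two-group SE | Two-group 95% interval | Actual two-sided alpha (nominal 5%) |
|---|---|---|---|
| -0.1 | 1.04 | about 4% too narrow | 5.9% |
| 0 | 1.00 | correct | 5.0% |
| 0.1 | 0.96 | about 4% too wide | 4.1% |
| 0.3 | 0.87 | about 15% too wide | 2.5% |
| 0.5 | 0.77 | about 29% too wide | 1.1% |

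With dropout, at an assumed 63 shared boys (102 active, 67 placebo), the SE ratio at rho 0.3 moves only from 0.87 to 0.88.

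**Step 3: exposure.** Step 2 held exposure equal; the planned table does not. Take no drug effect, a 20% risk per 48 weeks and independent periods. A Sequence 1 boy's risk over 96 weeks is 1 - 0.8^2 = 36%. The active column then expects (70*0.20 + 35*0.36)/105 = 25.3% against 20% on placebo, a crude difference of +5.3 points with no drug effect. At a 10% risk the figure is +3.0 points, and at 40% it is +8.0.

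**Step 4: both together.** Simulated trials under no drug effect, 20% risk per 48 weeks and Sequence 1 followed for 96 weeks give the rate at which a two-group test with pooled variance flags harm for active overall (nominal 2.5%): 12.1% at rho 0, 9.6% at 0.1, 5.3% at 0.3 and 2.3% at 0.5. At rho 0.3, an unpooled two-group test gives about 7%. Clustering by boy on the crude risk difference gives about 11%, because it removes the excess variance and leaves the exposure bias.

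**Step 5: dose levels.** If all boys escalate as planned, each dose level also holds 105 boys with 70 shared, so the ratio in Step 2 applies again. Exposure differs in another way: 16 weeks per boy at 5 and at 20 mg/kg against 48 weeks on placebo. With a constant event rate and 20% risk per 48 weeks, the 16-week risk is 1 - 0.8^(1/3) = 7.2%. The crude difference under no effect is then 7.2 - 20 = -12.8 points, which leans towards apparent safety.

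**The case against.** The SAP does not say that an independent-samples method will be used. It is silent and defers to sponsor standards that a reader of these documents cannot see. That stands: the finding is an unspecified method whose ordinary default would be wrong, and it is not an error already written into the plan.

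The stakes are also limited. SAP 6.6.1 calls the safety analysis exploratory and asks for footnotes on interpreting p-values and intervals. Protocol 9.3.5 says adverse event data will be tabulated and listed without formal statistical analysis. The primary safety endpoints in Protocol 2.2.1 rest on Period 1, where the groups do not overlap, and ongoing safety decisions rest on unblinded review by the external data monitoring committee. This lowers the consequence. It does not make a displayed interval or p-value valid, and the SAP does not guarantee a Period 1 risk difference for tier-1 events or for the less common tier-2 events.

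A reader might infer that the overlap makes real harms harder to detect. The documents do not support that. It needs positive rho, which is plausible but stated nowhere; with negative rho the intervals are too narrow. For active overall, Sequence 1's extra exposure also pushes the other way, and in Step 4 the two-group test over-flags harm at low to moderate rho.

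**Conclusion.** The point holds as a gap in specification with a calculable consequence. As planned, the complete-study active and placebo columns share 70 boys, the SAP requires intervals and tier-1 p-values on that contrast, and it names no method that accounts for the sharing. Under two-group output the variance is wrong whenever rho is not zero. The interval is about 4% to 29% too wide for rho from 0.1 to 0.5, and about 4% too narrow at rho -0.1. These sizes assume equal risk, equal exposure and the planned numbers; rho is an assumption throughout.

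The net direction of error in the planned table is not established, because unequal exposure acts on the same estimate: towards apparent harm for active overall, and towards apparent safety at 5 and 20 mg/kg. It follows that modelling the pairing alone is not a sufficient repair.

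**What to change.** Add to SAP 6.6.1:

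(a) For any table that pools Periods 1 and 2, state that Sequence 2 and 3 subjects contribute to both columns. Compute confidence intervals and tier-1 p-values with subject as the cluster (GEE with robust variance, or a bootstrap of subjects within sequence), for active overall and for each dose level. Do this on an exposure-equalised or exposure-adjusted scale (rate difference per subject-time, or equal-length windows), not on the crude risk difference.

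(b) Present the randomised, non-overlapping Period 1 comparison (Sequences 1 and 2 against Sequence 3, 70 against 35) for all tier-1 and tier-2 events, using independent-samples methods.

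Also correct the reference to section 8.2.3 in SAP 3.5.1.

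The cost is SAP text and programming, with no new data, visits or patients. The default output cannot be used for the pooled tables, and sparse events may need the bootstrap. Period 1 alone has less power. For 10% on placebo against 20% on active, the standard error is sqrt(0.1*0.9/35 + 0.2*0.8/70) = 0.070, giving about 30% power with an unpooled Wald test (23% with a pooled null variance). The 105-against-70 comparison has about 47% on the same unpooled test at rho 0 and equal exposure. A correctly analysed pooled table is therefore still worth keeping beside the Period 1 table.
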